8.3.3.2 Relationship to Study Intervention

All adverse events (AEs) must have their relationship to study intervention assessed by the site investigator (clinician) who examines and evaluates the participant based on temporal relationship and his/her clinical judgment. The degree of certainty about causality will be graded using the categories below. In a clinical trial, the study intervention must always be suspect.

- **Definitely Related (Definite)** – There is clear evidence to suggest a causal relationship, and other possible contributing factors can be ruled out. The clinical event, including an abnormal laboratory test result, occurs in a plausible time relationship to study intervention administration and cannot be explained by concurrent disease or other drugs or chemicals. The response to withdrawal of the study intervention (dechallenge) should be clinically plausible. The event must be pharmacologically or phenomenologically definitive, with use of a satisfactory rechallenge procedure if necessary.
- **Probably Related (Probable)** – There is evidence to suggest a causal relationship, and the influence of other factors is unlikely. The clinical event, including an abnormal laboratory test result, occurs within a reasonable time after administration of the study intervention, is unlikely to be attributed to concurrent disease or other drugs or chemicals, and follows a clinically reasonable response on withdrawal (dechallenge). Rechallenge information is not required to fulfill this definition.
- **Potentially Related (Possible)** – There is some evidence to suggest a causal relationship (e.g., the event occurred within a reasonable time after administration of the trial medication). However, other factors may have contributed to the event (e.g., the participant's clinical condition, other concomitant events). Although an AE may rate only as "possibly related" soon after discovery, it can be flagged as requiring more information and later be upgraded to "probably related" or "definitely related", as appropriate.
- **Unlikely to be related** – A clinical event, including an abnormal laboratory test result, whose temporal relationship to study intervention administration makes a causal relationship improbable (e.g., the event did not occur within a reasonable time after administration of the study intervention) and in which other

drugs or chemicals or underlying disease provides plausible explanations (e.g., the participant's clinical condition, other concomitant treatments).

- Not Related (Unrelated) – The AE is completely independent of study intervention administration, and/or evidence exists that the event is definitely related to another etiology. There must be an alternative, definitive etiology documented by the clinician.]

8.3.3.3 Expectedness

Site Investigators will be responsible for determining whether an adverse event (AE) is expected or unexpected.

An AE will be considered unexpected if the nature, severity, or frequency of the event is not consistent with the risk information previously described for the study intervention.

8.3.4 Summary of AE Reporting Requirements for Site Investigators

8.3.4.1 Adverse Event Reporting

All Adverse Events CTCAE Grades 1 and 2 should be entered into the eCRF within 14 days of discovery by the site if possibly, probably, or definitely related to the study treatment in the opinion of the site investigator.

All Adverse Events CTCAE Grade 3 and higher should be entered into the eCRF within 14 days of discovery by the site.

8.3.4.2 Serious Adverse Event Reporting

All SAEs should be reported to the Coordinating Center within 24 hours of discovery by the site.

Per UF DSMB policy, all SAEs will be reported to the UFHCC Data Integrity and Safety Committee (DISC) within 5 days.

8.3.5 Time Period and Frequency for Event Assessment and Follow-Up

The occurrence of an adverse event (AE) or serious adverse event (SAE) may come to the attention of study personnel during study visits and interviews of a study participant presenting for medical care, or upon review by a study monitor.

Any medical condition that is present at the time that the participant is screened will be considered as baseline and not reported as an AE. However, if the study participant's condition deteriorates at any time during the study, it will be recorded as an AE.

Changes in the severity of an AE will be documented to allow an assessment of the duration of the event at each level of severity to be performed. AEs characterized as intermittent require documentation of onset and duration of each episode.

Study Staff will record all reportable events with start dates occurring any time after the start of study treatment for 30 days after the After Treatment Stop Visit. At each study visit, the investigator or his/her designee will inquire about the occurrence of AE/SAEs since the last visit. Events will be followed for outcome information until resolution or stabilization.

During Survival Follow-up, AEs and SAEs will not be collected. Only Progression status and survival outcomes will be monitored during this stage of the study.

8.3.6 Adverse Event Reporting

Adverse Events shall be recorded and entered into the eCRF within 14 days. The Coordinating Center will report the events to the DSMB for review per policy.

The site investigator is responsible for informing the local IRB of adverse events per local requirements.

8.3.7 Serious Adverse Event Reporting

The site investigator must report any serious adverse event, whether or not considered study intervention related, including those listed in the protocol, package insert, or device use manual to the Coordinating Center within 24 hours of discovery and must include an assessment of whether there is a reasonable possibility that the study intervention caused the event. Study endpoints that are serious adverse events (e.g., all-cause mortality) must be reported in accordance with the protocol unless there is evidence suggesting a causal relationship between the study intervention and the event (e.g., death from anaphylaxis). In that case, the investigator must immediately report the event to the Coordinating Center.

All serious adverse events (SAEs) will be followed until satisfactory resolution or until the site investigator deems the event to be chronic or the participant is stable. Supporting documentation of the event may be requested by the Coordinating Center and should be provided as requested.

8.3.7.1 Unanticipated Adverse Device Effect

The investigational device exemption (IDE) regulations define an unanticipated adverse device effect (UADE) as “any serious adverse effect on health or safety or any life-threatening problem or death caused by, or associated with, a device, if that effect, problem, or death was not previously identified in nature, severity, or degree of incidence in the investigational plan or application (including a supplementary plan or application), or any other unanticipated serious problem associated with a device that relates to the rights, safety, or welfare of subjects” (21 CFR 812.3(s)). UADEs must be reported by the clinical investigator to the Coordinating Center and the reviewing IRB, as described below:

Investigators are required to submit a report of a UADE to the Coordinating Center within 24 hours after the investigator first learns of the event.

The IDE Sponsor will conduct an evaluation of a UADE and will report the results of the evaluation to FDA, all reviewing IRBs, and participating investigators within 10 working days after the sponsor first receives notice of the effect.

The site investigator is responsible for informing the IRB of the UADE per local requirements.

The IDE sponsor will make reports to FDA as required by §812.150.

8.3.8 Reporting Events to Participants

If additional risks are identified, the protocol will be amended and Informed Consent Form revision(s) implemented.

8.3.9 Events of Special Interest

This section is not-applicable. There are no events of special interest for this study. All adverse events CTCAE Grade 3 and above, and serious adverse events shall be collected and reported as describe in this protocol.

8.3.10 Reporting of Pregnancy

Pregnancy of any female subject including pregnancies that occur in the female partner of a male study subject should be reported to the Coordinating Center within 24 hours of discovery. All pregnancies must be followed to outcome.

The subject will be withdrawn from the study and the site investigator will continue safety follow-up.

8.4 Unanticipated Problems

8.4.1 Definition of Unanticipated Problems (UP)

Unanticipated problems involving risks to participants or others includes, in general, any incident, experience, or outcome that meets all of the following criteria:

- Unexpected in terms of nature, severity, or frequency given (a) the research procedures that are described in the protocol-related documents, such as the Institutional Review Board (IRB)-approved research protocol and informed consent document; and (b) the characteristics of the participant population being studied;
- Related or possibly related to participation in the research (“possibly related” means there is a reasonable possibility that the incident, experience, or outcome may have been caused by the procedures involved in the research); and
- Suggests that the research places participants or others at a greater risk of harm (including physical, psychological, economic, or social harm) than was previously known or recognized.

This definition could include an unanticipated adverse device effect, any serious adverse effect on health or safety or any life-threatening problem or death caused by, or associated with, a device, if that effect, problem, or death was not previously identified in nature, severity, or degree of incidence in the investigational plan or application (including a supplementary plan or application), or any other unanticipated serious problem associated with a device that relates to the rights, safety, or welfare of subjects (21 CFR 812.3(s)).

8.4.2 Unanticipated Problem Reporting

The investigator will report unanticipated problems (UPs) to the reviewing Institutional Review Board (IRB) per local policy and to the Coordinating Center within 24 hours of discovery. The UP report will include the following information:

- Protocol identifying information: protocol title and number, PI’s name, and the IRB project number;
- A detailed description of the event, incident, experience, or outcome;

- An explanation of the basis for determining that the event, incident, experience, or outcome represents an UP;
- A description of any changes to the protocol or other corrective actions that have been taken or are proposed in response to the UP.

An investigator shall submit to the reviewing Institutional Review Board (IRB) a report of any unanticipated adverse device effect occurring during an investigation as soon as possible, but in no event later than 10 working days after the investigator first learns of the effect (21 CFR 812.150(a)(1) and to the Coordinating Center within 24 hours of discovery.

The IDE sponsor who conducts an evaluation of an unanticipated adverse device effect under 812.46(b) will report the results of such evaluation to the Food and Drug Administration (FDA) and to all reviewing IRB's and participating investigators within 10 working days after the sponsor first receives notice of the effect. Thereafter the IDE sponsor shall submit such additional reports concerning the effect as FDA requests (21 CFR 812.150(b)(1)).

8.4.3 Reporting Unanticipated Problems to Participants

If additional risks are identified, the protocol will be amended and Informed Consent Form revision(s) implemented.

9 CONTROL COHORT

This trial will include a control cohort that includes both historical and contemporaneous control patients. A minimum of 90 and a maximum of 100 patients will be enrolled in the control cohort. This is a non-interventional control group (data collection only). All patients in the control cohort will be enrolled at the same participating institutions. Risks associated with participation of the control cohort are minimal.

Historical controls will be gathered via chart review of patients completing chemo/RT after 1/1/2016 and before 5/20/2019; 5/20/2019 is the initial date of IRB approval for the coordinating center and first opened study site. Control patients completing chemo/RT after 5/20/2019 will be enrolled as contemporaneous controls.

Control subjects (contemporaneous or historical) will be enrolled via informed consent if consent is practicable. An IRB waiver of consent will be requested for historical control patients who may be deceased, no longer being followed or lost to follow-up.

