9.2 Control Cohort Inclusion Criteria

In order to be eligible to enroll in the control cohort, an individual must meet all of the following criteria:

- A. Willing and able to provide written informed consent or eligible for inclusion under an IRB-approved waiver of consent
- B. Male or female, 18 years or older

- C. Histologic confirmation of WHO Grade II or III astrocytoma
 - a. mixed oligoastrocytomas are permitted
- D. Mutational identity determined by CLIA-certified sequencing including:
 - a. IDH1/2 wildtype (i.e. lack of detectable mutations on the sequencing report, variants of unknown significance or non-synonymous single nucleotide polymorphisms deviating from wild-type sequence do not apply)
- AND
- b. TERT promoter mutation(s)
- E. Karnofsky performance status $\geq 70\%$
- F. Maximal safe resection
 - a. biopsy alone is allowed
- G. Completed standard chemoradiation and concurrent temozolomide and adjuvant temozolomide.
 - a. Patients with a tumor that was biopsied or resected in the past followed by observation only without definitive chemoradiation and/or chemotherapy given will be eligible, as long as: repeat maximal surgical resection (biopsy only allowed) has been performed, definitive temozolomide/RT treatment meets the criteria above, and adjuvant temozolomide treatment was given (or planned for the contemporaneous cohort)
- H. Candidate for adjuvant high dose temozolomide per investigator's clinical judgement (for the contemporaneous cohort)
- I. No evidence of early disease progression per RANO criteria upon completion of Chemo/RT and beginning adjuvant temozolomide

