9.5 Control Cohort Limited Data Collection

Data collected for the historical and contemporaneous control group will be distinct from data collected for interventional patients in this study, as described below. Data for control patients is designed to be collected exclusively from chart review.

All control cohort documentation should be uploaded into the eCRF within 45 days of collection. Data extracted from the medical record shall be defined as collected on the day of extraction.

1. Informed Consent or waiver
2. Demographics

3. Pathology
4. Date of and extent of operation (GTR, partial, or biopsy)
5. Summary of Concurrent Chemo/RT

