10 STATISTICAL CONSIDERATIONS

10.1 Statistical Hypotheses

- Primary Efficacy Endpoint: overall survival (OS)

Control arm: the control arm will consist of both historical and contemporaneous control patients. Historical controls will consist of TERT mutation-only astrocytoma patients treated and followed by the participating sites between January 1, 2016 and May 20, 2019. As described above, these patients will have received standard treatment and would have met first tier inclusion/exclusion criteria for the study. Data for these patients will be collected via chart review. Contemporaneous controls will also consist of patients who qualify for the trial and receive standard treatment but decide not to proceed with the Optune experimental treatment because of personal preference. This personal preference must be non-medical in nature. Based on clinical experience, most commonly this non-medical patient personal preference preventing Optune use will be unwillingness to shave his/her head and/or unwillingness to wear a visible medical device on his/her head most of the day.

- N = 90 patients total in an expected mixture ranging between 80 historical controls and 10 contemporaneous controls to 60 historical controls and 30 contemporaneous controls.
- Assumed median survival = 22 months (based on Figure 3A in Eckel-Passow et al [12])
- Follow-up = up to 60 months for the historical controls, up to 60 months for the contemporaneous controls

Experimental treatment arm: TERT mutation-only astrocytoma patients who will receive standard treatment plus TFields therapy at one of 15 participating centers.

- N = 90 patients

- Assumed accrual rate = 2.5 patients/month accumulated over 15 centers
- Accrual period = 36 months
- Follow-up period after the end of accrual = 24 months
- Assumed survival time distribution = Weibull with accelerating hazard and proportional hazards

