11.2.2.1 Control Cohort Enrollment Documentation Requirements

The following documentation is required for control subject enrollment. All documents should be uploaded into the eCRF within 45 days of enrollment.

1. Signed and dated Informed Consent Form
2. Documentation of consent checklist
3. Pathology Report including MGMT methylation status. If not feasible or indeterminate, must be stated. Indeterminate methylation status will be considered unmethylated.
4. Immunohistochemistry or next-generation sequencing Report (e.g. Foundation Medicine, TEMPUS, Caris, or similar CLIA-certified sequencing service)
5. Screening MRI Report; RANO forms are not required at time of enrollment.
6. Signed and dated enrollment checklist

Additionally, the following data shall be entered into the eCRF at enrollment and source documentation included:

- a. KPS
- b. Resection Summary
- c. Chemo/Radiation Summary

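### Deceased historical controls enter by consent waiver but reachable living ones only if they agree, so any refusal removes longer survivors and biases the OS comparison towards TTFields

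*Combined protocol and SAP*

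**What the plan says.** Section 9 sets the default route: "Control subjects (contemporaneous or historical) will be enrolled via informed consent if consent is practicable". It then adds an exception for part of the cohort: "An IRB waiver of consent will be requested for historical control patients who may be deceased, no longer being followed or lost to follow-up". Section 9.2 item A makes one of these routes a condition of eligibility: "Willing and able to provide written informed consent or eligible for inclusion under an IRB-approved waiver of consent". The data list in section 9.5 agrees, with "Informed Consent or waiver" as its first item.

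Section 11.2.2.1 does not agree. It begins "The following documentation is required for control subject enrollment", and its item 1 is a signed and dated consent form, with no mention of a waiver.

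Historical controls are "patients completing chemo/RT after 1/1/2016 and before 5/20/2019". They form most of the comparator: "N = 90 patients total in an expected mixture ranging between 80 historical controls and 10 contemporaneous controls to 60 historical controls and 30 contemporaneous controls". Section 10.2.1 compares OS by log-rank test. Stratification by MGMT status or extent of resection is optional there. The plan does not ask for consecutive case-finding, a log of eligible patients not enrolled, or a sensitivity analysis for how controls were selected.

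**The concern.** Historical controls are identified from charts when many have already died. Under sections 9 and 9.2, vital status at the time of approach decides the route of entry, and vital status is the primary endpoint. A deceased patient cannot refuse, but a living, reachable one can. Patients who refuse have by definition survived to the approach date, so leaving them out removes the right-hand part of the control survival curve.

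The result is a control arm that looks worse than the population it represents, and so a test that rejects too often when TTFields does nothing. Adjustment for baseline factors does not repair this, because selection is on the outcome itself.

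**Working it through.** **Inputs from the plan (sections 9, 10.1 and 10.2).** Control median 22 months; Weibull shape k = 2.0 (1.8 also considered); 90 experimental patients against 90 controls, with 80 + 10 to 60 + 30 historical and contemporaneous; experimental accrual 36 months plus 24 months of follow-up, so 24 to 60 months each; historical follow-up up to 60 months; one-sided log-rank test at 0.05.

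**Reproducing the plan's figure.** For a 6-month gain, HR = (22/28)^2 = 0.617 and |ln HR| = 0.482. With follow-up uniform on 24 to 60 months in both arms, expected deaths are 78.4 (control) and 67.6 (experimental). Power = Φ(0.482 / √(1/78.4 + 1/67.6) − 1.645) = Φ(2.906 − 1.645) = 0.896. Table 10 gives 0.894 for 90 + 0 controls, so the inputs are read correctly.

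**Assumptions the documents do not supply.** Day 0 is spread evenly over the historical window of about 40.6 months, starting about a month after chemoradiation. Approach is in January 2020 (just after the control cohort was added, in protocol version 2.1 of 16 December 2019), spread over 2020–2021, or spread over 2021–2022. A share c of living historical controls is enrolled; all deceased ones are.

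**How the mix shifts.** If a share a of candidates is alive at approach, the living share among those enrolled is ac / (1 − a + ac). With a = 0.20 and c = 0.5 this is 0.10/0.90 = 0.11 instead of 0.20. With a = 0.42 it is 0.21/0.79 = 0.27 instead of 0.42.

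**Simulated one-sided false-positive rate**, no treatment effect, k = 2.0, 20,000 trials per cell:

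| Approach (share alive) | Controls | c = 1 | 0.9 | 0.7 | 0.5 |
|---|---|---|---|---|---|
| January 2020 (42%) | 80 + 10 | 0.05 | 0.07 | 0.14 | 0.28 |
| 2020–2021 (20%) | 80 + 10 | 0.05 | 0.06 | 0.11 | 0.18 |
| 2021–2022 (7%) | 80 + 10 | 0.05 | 0.06 | 0.08 | 0.11 |
| January 2020 (42%) | 60 + 30 | 0.05 | 0.07 | 0.11 | 0.20 |
| 2020–2021 (20%) | 60 + 30 | 0.05 | 0.06 | 0.09 | 0.14 |
| 2021–2022 (7%) | 60 + 30 | 0.05 | 0.06 | 0.07 | 0.09 |

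With 80 + 10 controls and c = 0.5, the mean control median falls from 22.0 months to 20.1, 20.8 and 21.5 for the three approach dates. The Day 0 convention and simulation error move cells by about 0.01. For example, starting Day 0 at the end of chemoradiation makes 39% alive in January 2020 and gives 0.27 at c = 0.5.

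**Sensitivity.** Across k = 2.0 and 1.8, loss to follow-up of 0 or about 10% a year, and approach 48 to 66 months after January 2016, the rate with 80 + 10 controls is 0.07–0.11 at 80% enrolled, 0.11–0.21 at 60% and 0.12–0.30 at 50%. With approach at 78 months only 3% are alive, and it is 0.061 at 80% and 0.072 at 60%. Loss unrelated to prognosis adds nothing of its own: with all the living enrolled, the rate stays at 0.049–0.054.

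**If a single route were used instead** (80 + 10 controls, approach 2020–2021). Consent only, with 90% of the living agreeing, gives a control median of about 34 months and power near 0 for a 6-month gain. Waiver only, meaning the deceased alone, gives a control median of about 19.4 months and a false-positive rate of about 0.58.

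**The case against.** The strongest reply is that the size is assumed. The documents contain neither a consent rate nor an approach date. For data collection from charts that section 9 calls minimal risk, refusal or non-enrolment of half the living has no support in the text. At 90% enrolment the error is 0.06 to 0.07, and late chart review shrinks it at every rate. This stands as to size. It does not remove the mechanism, because the plan secures neither high consent nor late review.

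A reader might infer that patients lost to follow-up share in causing the bias, or that every living patient who does not answer or lacks capacity drops out. The documents do not support either. The waiver group in section 9 includes patients no longer followed or lost, who may be alive, and consent is required only where practicable. Admitting such patients by waiver reduces the imbalance, and they are censored in the analysis. Only reachable living patients who refuse are clearly excluded.

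The direction is also conditional. The waiver is only to be requested, and section 11.2.2.1 item 1 leaves no room for it. If it were refused, or that item were applied literally, the deceased would be shut out and control survival would look too long. Separately, the waiver does not cover contemporaneous controls, so any who die before consenting may be missed, which pushes the other way in that smaller group.

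**Conclusion.** The concern holds in this form. Under sections 9 and 9.2, entry of historical controls depends on vital status, and any refusal among reachable living patients shortens control OS in favour of TTFields. With 80 + 10 controls and k = 2.0, the one-sided error is about 0.06–0.07, 0.08–0.14 and 0.11–0.28 when 90%, 70% and 50% of the living are enrolled. It is nil if all agree.

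These figures rest on assumed consent rates and approach dates. They should not be read as the trial's actual error rate, nor the 50% column as the expected case. Nor can the direction be taken as certain while section 11.2.2.1 contradicts sections 9, 9.2 and 9.5: which section a site follows decides which way the control curve is distorted. The plan should be changed, because the comparator for the primary endpoint depends on it and the change is cheap.

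**What to change.** 1. In section 9, request the waiver for all historical controls, regardless of vital or follow-up status. Keep individual consent only for the optional tissue in section 9.5.
2. In section 11.2.2.1, change item 1 to accept either a signed consent form or a documented waiver, so that it matches sections 9, 9.2 and 9.5.
3. At every site, identify eligible historical patients consecutively and log those not enrolled, by vital status.
4. Where an IRB refuses the all-patient waiver, keep the mixed route at that site and report a sensitivity analysis for the living patients not enrolled. One option is to weight each enrolled living control by the inverse of the enrolled share among the living. Do not substitute a single route: the figures above show that consent only or waiver only is far worse than the mixture.

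With all eligible historical controls included, the simulated error returns to about 0.05. The cost is a broader waiver request, which an IRB may ask to have justified or may refuse, and a screening log. No extra patients or procedures are needed.
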